7.1 Intention-to-treat (ITT) set

The ITT set includes all subjects who have received study medication at least once and for whom efficacy data upon treatment are available.

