5 SCHEDULE OF ASSESSMENT AND PROCEDURES

5.1 Study Assessments

5.1.1 Response Assessments

Disease status will be assessed by bone marrow and peripheral blood analysis at the end of each 4-weeks induction and consolidation cycle. Disease status during maintenance will be evaluated by peripheral blood analysis at the end of each cycle and during follow-up after SCT every 3 months \pm 28 days. Bone marrow aspirate during maintenance and FU is required in case peripheral blood analysis is suspicious for progression of disease/relapse. Response is evaluated according to Döhner et al. criteria¹.

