8.2 Sample Size Calculation

The sample size calculation is based on the evaluation of response rates according to Fleming using the A'Hern (Sample size tables for exact single-stage phase II designs. Statist. Med. 2001;20:859-866.) extension.

In Fleming's procedure two response levels p_0 and p_1 are specified:

- the largest response proportion p_0 which, if true, would clearly imply that the treatment does not warrant further investigations (except for other types of administration, e.g. in standardized combinations); and
- the minimum required response level p_1 that would imply the treatment warrants further investigations.

The following characteristics were specified

- $p_0 = 0.30$
- $p_1 = 0.60$
- $\alpha = 0.05$ (one-tailed) and
- $\beta = 0.10$

$N=25$ patients should participate in the study to ensure a power of $1-\beta=0.90$ for the discrimination of p_0 and p_1 . According to Fleming the null hypothesis should be rejected if at least

$$r = \left\lceil Np_0 + Z_{1-\alpha} \sqrt{Np_0(1-p_0)} \right\rceil + 1$$

responses are observed (x^* denotes the nearest integer to). With p_0 and N defined as above and $Z_{1-\alpha} = (1 - \alpha)$ -quantile of the normal distribution = 1.645 at least 12 responders should be observed to show the efficacy as postulated.

Using the same approach in the 15 additional patients, submitted to an adapted drug regimen, the power will be 80% to discriminate a $p_0=30\%$ (expected CR rate) from a $p_1=65\%$ (meaningful increase in CR rate), if 8 out of 14 completed patients are considered as responders, with a one-tailed alpha error of 5%.

Alternatively, the power will be 90% to discriminate a $p_0=30\%$ from a $p_1=70\%$ again if 8 out of 14 completed patients are considered as responders, with a one-tailed alpha error of 5%.

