8.3.1 Intent-to-Treat Population

Intent-to-Treat Analysis Set (ITT): The ITT-population includes all subjects who have received study medication at least once and for whom efficacy data upon treatment are available.

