17.6 Appendix 6 – NCI-CTCAE version 4.03

17.7 Appendix 7- Response criteria in AML

Definitions of response criteria are based primarily on those given by Döhner et al.⁽¹⁾

Response criteria	Absolute Neutrophil count	Absolute Platelets count	Bone marrow Blasts (%)	Comments
Complete remission (CR)*	$>1.0 \times 10^9/L$ (1000/ μ L)	$>100 \times 10^9/L$ (100.000/ μ L)	<5	Absence of blasts with Auer rods; Absence of EMD; independence of red cell transfusion
CR with incomplete recovery (CRi) [†]	$<1.0 \times 10^9/L$ (1000/ μ L)	$<100 \times 10^9/L$ (100.000/ μ L)	<5	All CR criteria except for residual neutropenia or thrombocytopenia.
Morphologic leukemia-free state [‡]	NA	NA	<5	Absence of blasts with Auer rods; Absence of EMD; no hematologic recovery required
Partial remission (PR)	$>1.0 \times 10^9/L$ (1000/ μ L)	$>100 \times 10^9/L$ (100.000/ μ L)	5 to 25	Relevant in the setting of phase 1 and 2 clinical trials only; decrease of pretreatment bone marrow blast percentage by at least 50%
Cytogenetic CR (CRc) [§]	$>1.0 \times 10^9/L$ (1000/ μ L) or $<1.0 \times 10^9/L$ (1000/ μ L)	$>100 \times 10^9/L$ (100.000/ μ L) or $<100 \times 10^9/L$ (100.000/ μ L)	<5	Reversion to a normal karyotype at the time of morphologic CR (or CRi) in cases with an abnormal karyotype at the time of diagnosis; based on the evaluation of 20 metaphase cells from bone marrow
Molecular CR (CRm) ⁱ	No standard definition; depends on molecular target			

Treatment failure	
Resistant disease (RD)	Failure to achieve CR or CRi (general practice; phase 2/3 trials); or failure to achieve CR, CRi, or PR (phase 1 trials); only includes patients surviving ≥ 7 days following completion of initial treatment, with evidence of persistent leukemia by blood and/or bone marrow examination

Death in aplasia	Deaths occurring \geq 7 days following completion of initial treatment while cytopenic; with an aplastic or hypoplastic bone marrow obtained within 7 days of death, without evidence of persistent leukemia
Death from indeterminate cause	Deaths occurring before completion of therapy; or < 7 days following its completion; or deaths occurring ≥ 7 days following completion of initial therapy with no blasts in the blood, but no bone marrow examination available
Relapse [¶]	Bone marrow blasts $\geq 5\%$; or reappearance of blasts in the blood; or development of extramedullary disease

EMD extamedullary disease

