The sample size calculation ended up in 25 patients to be recruited to ensure a power of 90 % for the discrimination of p_0 and p_1 . In addition, 15 additional patients were submitted to an adapted drug regimen (flat dose 60mg of Selinexor instead of 40 mg /m² of Selinexor). Using a similar approach, the power will be 80 % to discriminate a $p_0=30$ % from a $p_1=65$ %, with a one-tailed α of 0.05 %.

6 Statistical hypotheses

The purpose of this study is to evaluate efficacy of Selinexor in patients with relapsed/ refractory AML by complete response rate (CR or CRi). The null-hypothesis to be tested is

H_0 : *The observed response rate is less or equal than 30 %*

against the alternative hypothesis

H_1 : *The observed response rate is over 30 %*

7 Analysis sets

A detailed subject classification document will be prepared in a Data Review meeting prior database lock. The document will assign patients to the respective analysis sets depending on the observed protocol violations.

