14.3.4 Other safety variables

- Table 14.3.4.1 Descriptive statistics of vital signs by visit
- Table 14.3.4.2 Change from baseline in vital signs
- Table 14.3.4.3 Descriptive statistics of body weight by visit
- Table 14.3.4.4 Change from baseline in body weight
- Table 14.3.4.5 Review of physical examination
- Table 14.3.4.6 Frequency tables for ECG by visit
- Table 14.3.4.7 Frequency tables for ECOG by visit

EudraCT No.: 2014-000526-37

Study Code: SAIL

Study Title: An Investigator-Initiated Study To Evaluate Ara-C and Idarubicin in Combination with the Selective Inhibitor Of Nuclear Export (SINE) Selinexor (KPT-330) in Patients with Relapsed Or Refractory AML

Addendum to Statistical Analysis Plan dated 2017Aug25

Addendum to Statistical Analysis Plan dated 2017Aug25

Date and version of the addendum: Version 1, 2018Apr04

Sponsor: GSO Global Clinical Research B.V.

Principal Investigator: [name]. [name], Hamburg

The addendum to the Statistical Analysis Plan was approved by:

10 Apr 2018

[figure not shown]
Date

Signature [name], [name]
CEO GSO Global Clinical Research B.V.
Medical Writer

SA
10 Apr 2018

94.18

Date

Signature [name]. [name],
University Hospital Hamburg-Eppendorf

1. Purpose of the addendum to SAP

The purpose of this addendum to the Statistical Analysis Plan (SAP) dated 2017Aug25 is to clarify the analysis of the primary endpoint and to add an analysis of the difference between the subgroups.

2. Analysis of the primary endpoint

The primary objective of the clinical trial is to determine the efficacy of Selinexor in combination with standard chemotherapy in patients with relapsed/refractory acute myeloid leukemia (AML) by determination of rate of complete remission (CR) or morphologic complete remission with incomplete blood count recovery (CRi), as defined by the recommendations on diagnosis and management of AML in adults from an international expert panel, on behalf of the European LeukemiaNet.

The primary endpoint is defined as the percentage of patients achieving a CR or CRi. Patients with morphologic leukemia free-state (MLFS) shall be included into the group of responders.

To determine the efficacy of Selinexor in combination with standard chemotherapy, the best response after Selinexor treatment shall be analysed, thus the best response after the induction cycle(s).

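### The ITT set depends on undefined on-treatment efficacy data, so treated patients who die or withdraw before the first response assessment can leave the denominators of the response rate and the early death rate

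*SAP*

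**What the plan says.** SAP 7.1: "The ITT set includes all subjects who have received study medication at least once and for whom efficacy data upon treatment are available". Protocol 8.3.1 attaches the same condition, "for whom efficacy data upon treatment are available", to having received study medication. Neither document defines the phrase.

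The passages that determine who meets the condition are these:

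- **Timing of assessment.** Protocol 5.1.1: "Disease status will be assessed by bone marrow and peripheral blood analysis at the end of each 4-weeks induction and consolidation cycle".
- **Primary variable.** Section 2 of the SAP addendum makes it the best response following induction, and adds: "Patients with morphologic leukemia free-state (MLFS) shall be included into the group of responders". A response after transplantation or another treatment may not be used.
- **Missing data.** SAP 8 rules out imputation. Neither SAP 12.1 nor the addendum says how a treated patient without an assessment is counted.
- **Set assignment.** SAP 7 leaves this to a subject classification document prepared at a data review meeting before database lock: "The document will assign patients to the respective analysis sets depending on the observed protocol violations".
- **Treatment failure.** Protocol Appendix 7 lists under this heading, among others, "Deaths occurring before completion of therapy". No set definition or denominator rule refers to it.
- **Flat-dose cohort.** Fifteen patients were added, but the power statement in Protocol 8.2 holds "if 8 out of 14 completed patients are considered as responders".
- **Early death rate.** SAP 19.2 tabulates it on ITT (Table 14.2.2.5) and PP (Table 14.2.2.6) only. PP requires completion of the treatment section.

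**The concern.** The set carries the ITT label but can be read as a response-evaluable set. A patient who dies or fully withdraws before the end of the first cycle has no marrow assessment and so no value for the primary variable. Such patients have no documented remission, so leaving them out removes only non-responders and can only raise the reported rate.

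The early death rate is exposed in a different way. On one reading, the set definition removes the events the endpoint is meant to count. PP removes deaths during treatment by construction, and ITT may remove those before the first assessment.

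The trial is open-label, and membership is settled shortly before database lock. The ambiguity would therefore be resolved when outcomes can already be known. SAP 12.1 reports a percentage and a Wilson interval, and both depend directly on the denominator.

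**Working it through.** **Inputs.** From Protocol 8.2 and SAP 5: p0 = 0.30, p1 = 0.60, one-sided alpha 0.05, beta 0.10, N = 25. From Protocol 8.2: cut-off 12 of 25, and 8 of 14 in the flat-dose cohort of 15. From the protocol synopsis: 40 patients in total. The number unassessed, the responder counts and the number of early deaths used below are assumptions, because the documents do not give them.

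**1. The plan's own figures.** The Protocol 8.2 formula gives 25 × 0.30 + 1.645 × √(25 × 0.30 × 0.70) = 7.5 + 3.77 = 11.27. The nearest integer is 11, and adding 1 gives 12. Exact binomial: P(X ≥ 12 | 25, 0.30) = 0.0442 and P(X ≥ 12 | 25, 0.60) = 0.922. For 8 of 14: alpha is 0.0315, and power is 0.816 at 65% and 0.907 at 70%. The stated design reproduces.

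**2. Reported rate and interval.** Assume 11 responders among 25 treated, with k unassessed patients dropped. The rate is 11/(25 − k).

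| k | Rate | Wilson 95% CI |
|---|---|---|
| 0 | 44.0% | 26.7 to 62.9 |
| 1 | 45.8% | 27.9 to 64.9 |
| 2 | 47.8% | 29.2 to 67.0 |
| 3 | 50.0% | 30.7 to 69.3 |

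Pooled, with 17 responders assumed: 17/40 = 42.5% (28.5 to 57.8) includes 30%, whereas 17/37 = 45.9% (31.0 to 61.6) does not.

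**3. Expected bias.** If the true rate over all treated is 30% and a fraction d are unassessed non-responders, the expected reported rate is 0.30/(1 − d). For d = 5, 10, 15 and 20% this is 31.6, 33.3, 35.3 and 37.5%.

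**4. False-positive rate at a true 30%, N = 25.** This depends on the decision rule used.

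- *Fixed count of 12 from the original 25:* dropping non-responders leaves the responder count unchanged, so the error stays at 4.4%.
- *Cut-off recomputed from the protocol formula at the remaining n:* it is 12 at n = 25, 24 and 23, and 11 at n = 22. Responders are Bin(25, 0.30), and each non-responder is dropped with probability d/0.7. The error is 4.8, 6.6, 9.7 and 13.7% for d = 5, 10, 15 and 20%. The documents do not say which N applies.
- *Wilson lower limit above 30%:* here exactly k non-responders are dropped. The error is 4.4, 4.3, 4.1 and 9.1% for k = 0, 1, 2 and 3, and 17.4% for k = 6. It is not monotone because counts are discrete.

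**5. Flat-dose cohort.** Eight responders are 8/15 = 53.3% of those enrolled but 8/14 = 57.1% of the completed patients in the power statement.

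**6. Early death rate.** Assume 4 early deaths among 40, with k of them before the first assessment and excluded. The rate is (4 − k)/(40 − k), which is 10.0, 7.7, 5.3, 2.7 and 0% for k = 0 to 4.

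**The case against.** The strongest reply is that deaths would stay in the set. The plan lists early death rate and overall survival among its efficacy variables, so a death on treatment is naturally efficacy data. Appendix 7 classes deaths before completion of therapy as treatment failure and rests on the same ELN source to which the addendum ties the endpoint. Such a patient then has a categorised outcome, not a missing one. Blood counts including leukemic blasts are scheduled twice weekly during induction, so few dosed patients would lack any on-treatment disease data. The 14 completed patients belong to a power assumption, not a set definition. Finally, all deaths are summarised in the safety section (Table 14.3.2.9).

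These points make exclusion of deaths less likely, but they do not settle it. No set or denominator rule adopts Appendix 7, and none says that a death or a blood count satisfies the condition. Patients who withdraw alive before assessment are not covered by Appendix 7 at all. The safety table shows that deaths are not lost from the report, but it does not correct the early death rate.

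It is also fair that the sizes are hypothetical. With 11 responders, dropping one or two patients leaves 30% inside the interval. The larger error rates need 15 to 20% unassessed, all of them dropped, and a recomputed cut-off that no document prescribes.

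**Conclusion.** The concern holds. As written, the set rule lets treated non-responders leave the primary denominator and lets early deaths leave the early death rate. Both effects favour the treatment.

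The size depends on a number the documents do not give. In the 25-patient example, three exclusions add 6 percentage points (44.0% to 50.0%) and move the Wilson lower limit across 30%. With 4 early deaths among 40, the early death rate could be reported as anything from 10.0% down to 0%, the lower end requiring all four to be excluded. The fixed 12-of-25 rule is not inflated if it is applied to the original 25, but the SAP does not restate that cut-off. If every treated patient had a response assessment, no result changes. The rule should be corrected because it bears on the primary denominator and would otherwise be interpreted with outcomes in view.

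**What to change.** 1. In SAP 7.1 and Protocol 8.3.1, delete the condition "for whom efficacy data upon treatment are available", so that the set is all patients who received at least one dose.
2. Add to SAP 12.1 that a treated patient without a documented response after induction counts as a non-responder, with response as the primary endpoint defines it, including the addendum's treatment of MLFS.
3. List the unassessed patients with the reason for each.
4. Tabulate the early death rate on all treated patients, state its time window (none is given now), and drop Table 14.2.2.6.
5. Report an evaluable-patient response rate only as a labelled sensitivity analysis.

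A separate minor point: SAP 7.3 makes membership of the safety set depend on a later safety measurement. Protocol 8.3.3 has no such condition, and SAP 13 includes all participants. Delete it.

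The cost is a few sentences and a rerun of a few tables. The addendum already calls for the response tables to be updated. The reported response rate may fall slightly and the early death rate may rise.

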7.2 Per protocol (PP) set

The PP set will consist of all randomized subjects who completed the treatment section (up to Visit 9) with no relevant protocol violations, detailed in the subject classification document.

7.3 Safety set

The Safety set will comprise all subjects who received at least one administration of the study medication at any dosage and who have a subsequent safety measurement available.

8 General statistical considerations

The aim of the study is to evaluate the effect of Selinexor in patients with relapsed / refractory AML by complete response rate (CR or CRi).

All background, primary and secondary efficacy variables, and safety variables will be summarized by visit and treatment group. In addition to absolute values, changes from baseline values will be summarized, if feasible.

Summary statistics will include at least the number of patients, mean, standard deviation, median, minimum and maximum for continuous variables, and frequencies and percentages for categorical variables. The results of statistical tests (including 95% CIs) will be included in the tables, when appropriate.

If the assumptions of the parametric statistical test are not met, the use of common transformations (e.g. logarithmic, square root) will be considered. Appropriate non-parametric methods will be used if normality assumptions are not met even after transformations.

In the statistical analyses a p-value less than 0.05 will be considered as statistically significant. If not stated otherwise, all tests will be performed as two-sided and two-sided 95% CIs will be produced for the treatment differences. No adjustments for the p-values will be made. Missing values will not be imputed in the analyses.

Subgroup analyses by dosing schedule (Selinexor / mm² vs. flat dose of Selinexor) will be conducted for all study data.

The table and figure plan is presented in Appendix 18.2.

9 Demographic and other baseline characteristics

All background and other baseline characteristics will be tabulated with descriptive statistics. Medical history and other medication will be summarized with frequency distributions. Tabulations will be conducted overall and by dosing schedule. No statistical tests will be carried out for any baseline measures between the dosing schedules.

10 Concomitant medication/treatment

Concomitant medication and treatments will be summarized overall and by dosing group using ATC classification.

11 Extent of exposure and compliance

The extent of exposure and treatment compliance will be summarized descriptively overall and by dosing schedule.

12 Analysis of efficacy

Descriptive statistics of all of the efficacy data will be presented overall and by dosing schedule and visit for the ITT and PP analysis sets.

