8.3.3 Safety Population

Safety Analysis Set (SAS): The SAS- Set will comprise all subjects who received at least one administration of study medication at any dosage and for any period of time.

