12.3 Additional analyses

The survival analyses (OS, RFS, EFS) will be repeated using a different censoring approach than presented in 12.2. The calculation will be otherwise similar as previously presented, except for patients receiving a stem cell transplant (SCT). For these patients, the patient is censored at the time of the SCT.

13 Analysis of safety

All subjects who have participated in the study will be included in the safety analysis.

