13.1 Adverse events

All adverse events occurring during the course of the trial and for up to 30 days after the last dose of study medication will be captured, documented and reported. The number of patients developing adverse experiences will be tabulated using [NCI CTCAE] Version 4.03. The CTC v4.03 will be the basis for grading the laboratory changes. Additionally, the subset of adverse experiences considered treatment-related will be summarized. Listings of adverse experiences leading to treatment discontinuation will be provided.

Clinical adverse events and laboratory adverse events will be reported in separate tables. The adverse events will be reported as a whole and additionally based on the severity grading (separate table for grade 3-5 AEs).

Adverse events classified as serious adverse events (SAEs) will be listed separately. Deaths together with the reason for death and the possible relation to study treatment will be summarized.

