13.3 Other safety variables

Vital signs (blood pressure, heart rate, temperature) will be summarized with descriptive statistics by visit and dosing group. In addition, the changes from baseline values will be given. The changes from baseline will be analyzed by ANOVA method if feasible. Physical examination, ECG and ECOG results will be summarized with frequency tables.

14 Completion and premature discontinuation

Completion and premature discontinuation will be listed. The reasons for premature discontinuation will be presented.

15 Deviations from the analyses planned in the study protocol

The primary hypothesis of the study was clarified in the Statistical Analysis Plan compared to the definition in the protocol.

16 Execution of statistical analyses

Statistical analyses will be performed by 4Pharma Ltd.

17 Hardware and software

Statistical analysis, tables and patient data listings will be performed with SAS[®] version 9.3 for Windows (SAS Institute Inc., Cary, NC, USA).

18 References

Clinical Study Protocol, Final Protocol, Version 2 (25.08.2015)

19 Appendices

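### SAP 7.3 makes entry to the Safety set depend on post-dose data, in conflict with Protocol 8.3.3 and SAP 13 and without declaring it; the effect is probably small and could go either way

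*SAP*

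**What the plan says.** Three places define who is analysed for safety.

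- Protocol 8.3.3 (Safety Population): "all subjects who received at least one administration of study medication at any dosage and for any period of time". Nothing is required after the dose.
- SAP 7.3 (Safety set): at least one administration of study medication "at any dosage and who have a subsequent safety measurement available". The protocol's closing words on duration are replaced by a condition on later data.
- SAP 13 (Analysis of safety): "All subjects who have participated in the study will be included in the safety analysis". This has no condition on later data and does not mention dosing.

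SAP 15 gives one deviation from the protocol: "The primary hypothesis of the study was clarified in the Statistical Analysis Plan compared to the definition in the protocol". The Safety set is not mentioned there or in the 2018 addendum. The SAP reference list cites "Clinical Study Protocol, Final Protocol, Version 2 (25.08.2015"), whereas the protocol supplied is Version 3.1.

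SAP 13.1 plans a death summary within safety: "Deaths together with the reason for death and the possible relation to study treatment will be summarized". In the table plan (SAP 19.2) the main efficacy tables carry an ITT or PP label. None of the safety tables in 14.3 carries a set label, including Table 14.3.2.9 on deaths.

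**The concern.** A safety denominator should be fixed by exposure alone. Once a patient also needs a later measurement to be counted, membership depends on the patient's course after dosing. Those without a later measurement are mainly the ones who died or were lost soon after the dose. SAP 8 states that "Missing values will not be imputed in the analyses", so nothing brings an excluded patient back.

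The SAP also gives the programmer two rules, 7.3 and 13, with no table label to choose between them. At stake are the adverse event proportions and the safety-section death summary. The SAP presents all data by dosing schedule as well as overall, in cohorts of 25 and 15, where one patient is visible in a percentage.

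**Working it through.** The plan states no figure on this point, so there is nothing to reproduce. The check is a comparison of the texts followed by an illustration.

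**Comparison**

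| Source | Dose required | Later data required |
|---|---|---|
| Protocol 8.3.3 | yes, at least one | no |
| SAP 7.3 | yes, at least one | yes, a safety measurement |
| SAP 13 | not stated | no |

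SAP 7.3 differs from the protocol and from SAP 13. SAP 15 and the addendum are silent on it.

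**What the added condition does**

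Let N be the number dosed, d the deaths among them, and k the dosed patients without a later safety measurement.

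*Case A: the k patients died and their death record is not counted as a safety measurement.* The proportion moves from d/N to (d − k)/(N − k), a fall of k(N − d) / [N(N − k)].

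N = 40 is the total in Protocol 3.2, made up of 25 + 15 in Protocol 8.2. The documents give neither d nor k, so both are assumed:

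| N | d | k | All dosed | SAP 7.3 | Fall (points) |
|---|---|---|---|---|---|
| 40 | 3 | 1 | 3/40 = 7.5% | 2/39 = 5.1% | 2.4 |
| 40 | 5 | 1 | 5/40 = 12.5% | 4/39 = 10.3% | 2.2 |
| 40 | 5 | 2 | 5/40 = 12.5% | 3/38 = 7.9% | 4.6 |
| 25 | 3 | 1 | 3/25 = 12.0% | 2/24 = 8.3% | 3.7 |
| 15 | 1 | 1 | 1/15 = 6.7% | 0/14 = 0.0% | 6.7 |
| 15 | 2 | 1 | 2/15 = 13.3% | 1/14 = 7.1% | 6.2 |
| 15 | 3 | 1 | 3/15 = 20.0% | 2/14 = 14.3% | 5.7 |

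Check of the first row: 1 × 37 / (40 × 39) = 37/1560 = 2.4 points. In the 15-patient cohort the fall is 6.7 points only when the excluded death is the sole one.

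*Case B: the k patients were lost with no recorded event.* With x patients having an adverse event, x/N becomes x/(N − k), which is a rise. For an assumed x = 30, 30/40 = 75.0% becomes 30/39 = 76.9%.

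The direction therefore depends on why the later measurement is missing.

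**How likely k > 0 is**

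The protocol synopsis has toxicity graded twice weekly during treatment, and Protocol 6.5.1 says most patients are in hospital for induction. During induction the gap to a first measurement is a few days.

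The optional single Selinexor dose before induction is less well covered. In the schedule (Protocol 5.2, Table 2) the Baseline column holds only that dose and the research marrow samples, and Protocol 5.1.3 starts adverse event monitoring at cycle 1 day 1. Serious events are reportable from consent (Protocol 7.2), but death from progression is not classed as serious (Protocol 7.1.4).

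**The case against.** The strongest reply is that the clause has little or no practical effect. SAP 4 lists adverse events among the safety variables, so a recorded fatal event can naturally be read as a safety measurement, and that patient stays in. With twice-weekly grading, almost every dosed patient will have something recorded. The mortality results readers will look at first, early death rate and overall survival, are efficacy variables tabulated on ITT and PP, so SAP 7.3 cannot change them. All of this stands as a limit on size. It does not settle the wording, because the SAP never says what counts as a safety measurement.

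A reader might infer that SAP 7.3 removes the patients with the worst early course and so biases adverse event and death rates downward. The documents do not support this as a general statement. It needs an excluded patient who had an event, and an event record that does not count as a measurement. For a patient lost without events the bias runs upward.

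A reader might also infer that SAP 13 brings undosed patients into the safety analysis. Its wording allows that, but in a safety section it can equally mean treated patients, in which case it agrees with Protocol 8.3.3.

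Finally, the SAP cites protocol Version 2, whose Safety set wording is not available, so a departure from that version cannot be shown. However, the addendum dates the SAP 25 August 2017, after Version 3.1 (13 January 2017). The conflict between SAP 7.3 and SAP 13 does not depend on the protocol version.

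**Conclusion.** The conflict is real and should be corrected. SAP 7.3 sets a narrower Safety set than Protocol 8.3.3 and SAP 13, ties inclusion to post-dose data, is not declared as a difference from the supplied protocol, and is not resolved by the table plan. Confidence in the textual mismatch is high. Confidence in any particular bias is not, because the documents give no count of dosed patients without a later measurement and no definition of a safety measurement.

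The likely effect is small. Under the assumptions of Case A, with one excluded death, it is about 2 points on 40 patients and about 6 to 7 points on the 15-patient cohort. It is zero if every dosed patient has a later record. It reaches the safety-section tables only.

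**What to change.** Make the change by SAP addendum, since the initial analysis has already been run (addendum, section 3):

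1. In SAP 7.3, delete the condition on a subsequent safety measurement, so that the set matches Protocol 8.3.3.
2. Make SAP 13 refer to that set and label the tables in 14.3 with it.
3. Record the change under SAP 15 and cite the protocol version that applies.
4. State separately whether the optional baseline Selinexor dose counts as study medication for this set. Protocol 8.3.3 does not say. The answer must be reconciled with the start of adverse event collection in Protocol 5.1.3; otherwise a patient given only that dose could enter the denominator without non-serious events having been collected.
5. Report how many dosed patients SAP 7.3 excluded, overall and by dosing schedule. The subject classification document (SAP 7) and Table 14.1.3 should allow the count.

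The cost is a few sentences and one count. No new data are needed, and the safety tables are rerun only if the count is above zero.
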